10.1 Socioeconomic context and inequalities

Young offenders often lead chaotic lives and face complex problems, including substance use, unsuitable accommodation and emotional or mental health issues. Literacy levels are unacceptably low and the vast majority has in the past been excluded from school [3]. As a result of the above risk factors, the list of negative consequences that result from substance use by young people is extensive and includes physical, psychological and social problems in both the short and long term. Furthermore, young people who offend experience a range of complex multiple risks and vulnerabilities including, neglect and abuse [8], substance use and related problems [9, 10] and exclusion from school [11]. Research has shown that young people who offend are more likely to experience a range of inequalities in later life, for example poorer physical health [9], early pregnancy in females [12] and higher rates of tobacco use and drug and alcohol dependence [5, 10, 11], reduced employment chances and economic hardship [13]. Indeed, there is widespread agreement that young people who offend are at increased risk of health and social problems making them one of the most vulnerable and often 'hard to reach' populations in the UK [14], which has one of the highest youth custody populations in western Europe [15].

10.2 Inclusion criteria: Young people aged 13 to 17 years inclusive, engaged with the criminal justice system in the youth offending service and on a community order, scoring 2 or more on the ASSET tool, ASSET Plus or equivalent on the substance use domain, able and willing to provide informed consent.

10.3 Exclusion criteria: Severity of substance use requiring immediate referral to specialist services, known criminal justice involvement likely to lead to incarceration during the intervention or follow-up period, currently on an order with substance use abstinence as a pre-requisite.

11. Trial Procedures

11.1 Training: Existing intervention staff will be augmented with new staff in locations where RISKIT is not currently available, North East England. Existing experienced youth workers, employed by KCA/Addaction, will be trained using an existing training package by training staff from the South East area. The training is provided over two days and covers; theoretical underpinnings, delivering programme elements, managing groups, individual motivational interviews, managing risks and safeguarding. A full intervention manual, covering training and practice, is available for interventionists; senior practitioners will observe practice and deem practitioners as competent prior to embarking on the RISKIT programme. Supervision is provided by senior staff with experience of delivering the intervention throughout the study period. In addition, all interventionists will attend a half-day training session on trial procedures and outcome assessment prior to the start of recruitment.

11.2 Control Intervention: Guidelines suggest that interventions should be provided for adolescents within CJS settings who score 2 or more on ASSET, ASSET Plus or equivalent for substance use. But the reality is that those with no immediate clinical need for treatment, in the form of detoxification or substitution are unlikely to receive an intervention, rather existing services are signposted and rates of engagement are low [6]. When intervention is provided it often takes the form of short duration brief behavioural change interventions with limited evidence of effectiveness in substance using population [39].

12. Randomisation: Allocation conducted at the level of the participant and conducted independent of the research team using random permuted blocks of variable length. Randomisation strings are generated by Codeface Ltd and encrypted and stored within the baseline data collection tool. To allow for the most efficient use of resources differential allocation will be employed with twice as many participants allocated to the control group compared with the intervention group. Power calculations have been adjusted to reflect the allocation ratio. Allocation will include stratification by gender, Youth Offending Team (YOT) and age (13-15 years versus 16-17 years).

12.1 Flowchart of study

14/183/02 RISKIT-CJS Flow chart

13. Screening for the trial: All adolescents within YOT are routinely screened using the ASSET tool. Trained researchers will liaise with staff within YOT to identify potential participants scoring 2 or more on the substance use section of ASSET, ASSET Plus or equivalent and arrange to meet with them at a scheduled appointment.

13.1 Intervention fidelity: The process will be assessed through recording interventions delivered and an assessment of intervention fidelity. Analysis of fidelity will include the proportion of allocated sessions attended and assessment of fidelity to session content analysed independently using the BECCI index.

Months 1 – 6	Initial set-up, recruitment of centres, staff training,
	ethics
Month 7 – 18	Participant recruitment
Month 9 – 21	Qualitative research interviews
Month 12 – 24	6 month follow-up
Month 18 - 30	Month 12 follow-up
Month 30 – 33	Effectiveness, economic and criminal justice analysis
Month 33 - 36	Writing report and dissemination of results

14. Project timetables and milestones

15. Statistical considerations

15.1 **Sample size calculation:** For the effectiveness analysis is designed to identify a clinically important difference of 0.3 for the primary outcome measure, percent days abstinent from all substances at 12 months post-randomisation in addition to a clinically important difference of the secondary outcome measure of mental health wellbeing, measured using the WEMWBS. In order to detect an effect size difference of 0.3, with alpha of 0.05 at 80% power using a two-sided test requires 175 analysed at 12 months in each of the two groups, a total of 350. As the intervention is intensive and potentially costly to implement we have increased the efficiency of the study by allocating participants in a 2:1 ratio, with twice as many allocated to the control condition. As differential allocation leads to a loss of power we have maintained the integrity of the sample size calculation by increasing the numbers required; 264 in the control group and 132 in the intervention group, a total of 396. Our previous studies with adolescents and those involved in the criminal justice system (SIPS-CJS, RISKIT) suggests that loss at 12 months is likely to be somewhere in the region of 15 to 30% and we have adjusted the required sample to account for a 30% loss at 12 months. This inflates the required number to 567; 378 in the control group and 189 in the intervention group. Between 2013 and 2014 the mean number of potentially eligible participants across the participating regions was 5200, with a prevalence of ASSET score 2 or more ranging between 32 and 42%, of these we estimate 80% will meet all other eligibility criteria. Based on these estimates we require a consent rate of the order of 40% in order to achieve our estimated sample size estimation over the recruitment period. Our experience in the feasibility study suggests that 60% of those eligible are likely to consent.

The qualitative component of the study will be purposive and include group discussion with participants in the intervention group and individual interviews with staff in participating YOT's. Participants will be chosen purposively in order to provide diversity in terms of site, and age and ensure appropriate participation by gender, social class and ethnicity. The sample size considerations of the qualitative component are driven by the need to achieve data saturation, the point at which no new themes are emerging from the data, and this

needs to be judged in practice. Our previous experience of similar studies estimate the participants needed to be of the order of 12 groups and the number of staff in YOT to be of the order of 24.

15.2 Effectiveness analysis: Effectiveness analysis will be conducted by treatment allocation using a two-sided 5% significance level. Analysis and results will be presented in accordance with CONSORT guidelines. The primary outcome is percent days abstinent from substance use in the 28-days prior to the 12-month follow-up. After checking for distributional assumptions and making any appropriate transformations this will be analysed using an analysis of covariance adjusting for baseline values and stratification values used in the allocation process; age, gender and centre. Results will be presented as mean differences between the groups and the associated 95% confidence intervals. Missing data will be assessed using multiple imputation approaches to model missing data scenarios and sensitivity analysis will be conducted to explore the relative impact of missing data on the observed outcome. Secondary outcomes will be analysed in a similar manner.

Analysis will also be undertaken to model the relationship between pre-randomisation factors and observed outcome at 12-months; demographics, self-efficacy, readiness to change. This analysis will employ a linear regression model including interaction terms for allocated group. To further enhance our understanding, we will additionally incorporate an analysis of process by enhancing the prognostic analysis by including measures of adherence, fidelity, derived from the BECCI ratings, and therapeutic alliance.

Exploratory sub-group analysis will be undertaken to model the relationship between gender, ethnicity and social class measured using index of material deprivation from postcode on observed outcome.

15.3 Cost-effectiveness analysis: The effectiveness analysis will be complemented by an economic evaluation that will evaluate the economic implications of the intervention versus treatment as usual. Substance use generates high costs for the individual, health service and society in general and the economic analysis will be conducted first using a narrow health and social care perspective, to concord with NICE guidelines for the conduct of health economic evaluations and second using a wider public sector perspective incorporating costs associated with employment, training, education and criminal justice.

The costs associated with identifying the eligible population and delivering the interventions will be estimated by prospectively monitoring local costs associated with this activity and micro-costing training, management, supervision, facilities and associated overheads. Data will be extracted from study billing records. Impact on service use on the part of the participant will be estimated using a specifically designed CSRI and units of service use valued using national sources of information.

The economic analysis will comprise cost-consequences analysis (CCA), incremental costeffectiveness (CEA), and cost-utility analyses (CUA). The CCA will report mean and confidence intervals of: primary and secondary outcomes as described above as well as the quality-adjusted life years (QALYs) gained, costs per participant in each arm, and differences between arms. The CEA will comprise calculation of the incremental cost per incremental day free of substance use, and the CUA, incremental cost per QALY gained. QALYs will be calculated from CHU-9D data converted to health state utilities using preference weights specific to the UK population and integrated over time. A sensitivity analysis calculating EQ5D-5L-based QALYs will also be conducted. All analyses will be conducted over the time horizon of one year. Analysis of uncertainty will comprise reporting of standard errors and/or 95%CIs around increments and calculation of the costeffectiveness acceptability curve. Non-parametric bootstrapping will be employed to investigate joint uncertainty in costs and effects and both one-way and multi-way sensitivity analysis will be conducted to explore the impact of our basic assumptions. The study will be conducted and reported in accordance with good practice guidelines for health economic evaluations [40].

15.4 Criminal justice outcomes: Criminal justice outcomes will be analysed using a combination of linear and logistic analysis of covariance to explore changes between groups and associated differences. A secondary analysis of CJS data will incorporate baseline risk assessments to explore the potential intervention effects on participant risk status.

15.5 Qualitative analysis: The aim of the qualitative component of the proposal is to explore participants' and practitioners' experience of the RISKIT-CJS intervention in order to generate information pertaining to the feasibility, acceptability, contextual influences and mechanisms of action. The qualitative design consists of two elements; the first is participatory group work with participants who have experienced the RISKIT-CJS programme and the second telephone interviews with practitioners who work with these participants. Thematic coding of qualitative data will be carried out using specific software (QSR NVIVO) that allows for the coding of both verbal, transcripts and field notes, and visual data. The coding allows for the identification of recurrent and important themes and the generation of a framework of themes relating to the key research questions and objectives. A detailed description of themes will be presented. Emergent themes that may be explored from the quantitative data analysis will be incorporated into the analysis plan as secondary exploratory analyses.

16. Compliance and withdrawal

16.1 Assessment of compliance: Visits to the individual YOT's in the geographical sites will be conducted by research staff to ensure compliance with protocols.

16.2 Withdrawal of participants: Participants have the right to withdraw from the trial at any stage. Reasons for withdrawal will be recorded. Participants can withdraw from the study completely, whereby all trial data previously collected will be deleted. They may withdraw from the study partially whereby no further data collection will be undertaken. They may withdraw from any allocated intervention but agree to adhere to any future follow-ups.

17. Data monitoring, quality control and quality assurance

This is a low risk trial. The University of Kent and the /NIHR PHR Programme have therefore agreed that the TSC will also monitor trial data in place of a separate Data Monitoring and Ethics Committee (DMEC). To this end, independent members may access unblended study data and meet in closed session. The main areas of focus will include informed/consent, recruitment, data quality and completeness of documentation.

Following the initial meeting, the TSC will meet annually. Its role is to oversee the trial to ensure it is conducted to high standards in accordance with the protocol, the principles of Good Clinical Practice (GCP) applied to non-drug trials, and relevant regulations and guidelines. This committee will also take responsibility for the ethical compliance of the trial. The purpose of this committee will be to monitor efficacy and safety endpoints, although only independent members may have access to unblinded study data. Written Terms of Reference will be agreed by the TSC. All monitoring findings will be reported and followed up with the appropriate persons in a timely manner. The study may be subject to inspection and audit by the University of Kent under their remit as sponsor, and other regulatory bodies to

ensure adherence to GCP. The investigators' institutions will permit ethical review, trialrelated monitoring and audit, and regulatory inspection(s), and provide direct access to source data and documents.

All monitoring findings will be reported and followed up with the appropriate persons in a timely manner. In case of adverse events deemed a serious, the chair of the TSC will form an extraordinary DMEC, where members who will follow good practice guidelines in assessing the relationship between events and the process of the trial and take any appropriate action. The study may be subject to inspection and audit by the University of Kent under their remit as sponsor, and other regulatory bodies to ensure adherence to GCP. The investigators/ institutions will permit trial-related monitoring, audits, ethical committee review and regulatory inspection(s), providing direct access to source data/documents.

18. Adverse event monitoring and reporting: Due to the nature of the study it is not expected that participants will experience any adverse events/serious adverse events during the study. In the event that the participant reports an event related to the study during a study visit this will be reported on an adverse event form and fully investigated by the CI. Each site principal investigators will assess the adverse even following the CONSORT guidelines[41] (see annexe). All adverse events will be reported to the TSC chair.

19. Ethics and regulatory issues: As participants are not being recruited from the NHS, the proposed research will not require NHS ethical approval but we will seek multi-site ethical approval from the University of Kent ethics committee, which covers all non-NHS studies carried out at the University. Information sheets will be provided to all eligible subjects and written informed assent/consent obtained prior to any study procedures.

20. Research governance: The University of Kent will be the nominated sponsor of the study. A dedicated trial manager under the supervision of the chief investigator will manage the day-to-day conduct of the study. A trial management group consisting of all principal investigators, research staff, named collaborators and at least one lay member will meet monthly to monitor conduct of the trial and address any issues arising. In addition, the study will be overseen by a trial steering committee, with an independent chair, expert and lay members and a separate data monitoring and ethics committee. The study will be conducted in accordance with the Data Protection Act and the Freedom of Information Act and will be conducted in accordance with the Medical Research Councils Guidelines on Good Clinical Practice in Clinical Trials and will include compliance with appropriate ethical approval and the Declaration of Helsinki.

21. Confidentiality: All data generated from the study will be stored in a secure environment and identified only by a unique participant identifier. The master registry, containing the link between personal information and the identifier, will be maintained in a separate secure environment and data linked only for the purpose of follow-up. No personal identifiable information will be kept beyond the 12-month follow-up point unless prior consent for longer-term follow-up has been received. For the purposes of this proposal analytical datasets will not contain any personal information.

22. Insurance and finance: Indemnity in respect of potential liability arising from negligent harm relating to design and conduct of the research is provided by the University

of Kent for those researchers who have their substantive contracts of employment with the University of Kent. Researchers not employed by the University of Kent will be indemnified by their current institution. This is a non-commercial study and there are no arrangements for non-negligent compensation. NIHR Public Health Research Programme is funding the study.

23. Study report/publications: The data will be the property of the Chief Investigator and Co-applicants. Publication will be the responsibility of the Chief Investigator. It is planned to publish this study in peer review articles and to present data at national and international meetings. Results of the study will also be reported to the Sponsor and Funder, and will be available on their web site. All manuscripts, abstracts or other modes of presentation will be reviewed by the TMG prior to submission. Individuals will not be identified from any study report.

During the study we aim to present the design, aims and findings to audiences at a number of subject specific international conferences. We will also plan an end of study forum, organised in collaboration with the University of Kent that brings together all elements of the research team to discuss the interpretation of the study across a variety of stakeholder groups. Throughout, and after the study, we aim to develop and maintain a website, with portals specifically designed for different audiences placing the results of the study in the wider context of intervention work in the fields of youth justice and adolescent health. A full manualised training and intervention package will be developed in collaboration with Addaction and made available to other service providers. Using our experience of implementing RISKIT in school settings we will also provide a matrix of appropriate implementation strategies across the youth justice environment.

A short version of the protocol has been submitted and published in BMC Public Health in 2017[42].

References

- 1. Odgers, C.L., et al., *Is it important to prevent early exposure to drugs and alcohol among adolescents?* Psychol Sci, 2008. **19**(10): p. 1037-44.
- 2. Newbury-Birch, D., et al., *Alcohol-related risk among young offenders aged 11-17.* Int Jnl of Prisoner Health, 2015. **in press**.
- 3. Youth Justice Board. and Ministry of Justice., *Youth Justice Statistics 2012/13. England and Wales*. 2014: London.

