In order to assess potential prognostic factors, in addition to demographics, that may impact on outcome Readiness to change, measured using the Readiness to change questionnaire, (RCQ-TV), and self-efficacy, measured using the Situational Confidence Questionnaire, (SCQ) will be measured at baseline. Both instruments are relatively short self-completed questionnaires with established psychometric properties in the adolescent population.

The process of delivering the intervention may also play a role in the outcomes observed in the intervention group and we aim to assess this process using two distinct approaches. First, at the end of the intervention we will ask each participant to rate the intervention using the Therapeutic Alliance Scale for Children (TASC-r; [34]) a 12-item self-completed questionnaire with established psychometric properties in the adolescent population. Second a random sample of 20% of individual motivational interventions, stratified by centre, age

and gender, will be recorded and assessed by independent raters using the Behavioural Change Counselling Index (BECCI; [35]) to assess fidelity and quality of interventions delivered.

The economic outcome measures will address the costs of delivering the interventions, changes in health utility in the 12 months after randomization and the costs associated with participants in the 12 months after randomization. Costs associated with delivering the intervention will be derived using a micro-costing approach accounting for the actual costs including associated training, facilities, overheads and management costs. Health utility will be assessed using the self-completed 5-item EQ5D-5L and 9-item CHU-9D assessed at baseline, 6 and 12 months. Service utilization on the part of the participant will be assessed using a specifically designed client receipt service inventory (CRSI, [36]) currently being piloted with the adolescent population. Service use will be assessed from a wide public sector perspective encompassing health and social care; criminal justice, education and employment service utilisation.

Criminal justice outcomes will include arrests, charges and convictions and will be derived from both Police National Computer (PNC) Systems and YOT Management Information Systems (YOT-MIS). Data will be collected for all offence types for the 12 months prior to and 12 months after randomization. In addition, data on offences, court appearances and sentencing occasions.

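### Linear ANCOVA under 2:1 allocation makes no allowance for unequal arm variances; robust standard errors would be a cheap, low-priority safeguard

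*Protocol*

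**What the plan says.** Section 12 of the protocol sets an unequal allocation, with "twice as many participants allocated to the control group compared with the intervention group". Section 15.1 carries this into the sample size: 264 control and 132 intervention participants analysed (396), or 378 and 189 randomised (567) after 30% loss.

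For the primary outcome, percent days abstinent at 12 months, section 15.2 plans that "this will be analysed using an analysis of covariance adjusting for baseline values and stratification values used in the allocation process", naming age, gender and centre. The step before the model is "After checking for distributional assumptions and making any appropriate transformations". The reporting scale is fixed: "Results will be presented as mean differences between the groups and the associated 95% confidence intervals". It adds: "Secondary outcomes will be analysed in a similar manner".

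Section 9.4 states: "Criminal justice outcomes will include arrests, charges and convictions". Section 15.4 states: "Criminal justice outcomes will be analysed using a combination of linear and logistic analysis of covariance". It does not say which of these outcomes is treated as a count in the linear model and which as binary in the logistic model.

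The protocol nowhere mentions robust or unequal-variance standard errors. It also nowhere states that a single pooled variance will be used. It gives no standard deviation by arm and no mean or dispersion for arrests, charges or convictions.

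**The concern.** Ordinary ANCOVA estimates one residual variance and applies it to both arms. With equal arms, the resulting standard error for the treatment difference is right on average even if the arm variances differ. With 2:1 allocation it is not. The true variance of the difference gives the intervention arm's variance twice the weight of the control arm's, while the pooled estimate does the reverse.

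The outcomes are of a kind where variance tends to move with the mean: a percentage bounded at 0 and 100, and possibly event counts. If the intervention lowers event counts, variance falls in the smaller arm. The ordinary standard error is then too large, and some real effects are missed. If the smaller arm is the more variable one, the interval is too narrow.

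The 2:1 ratio has been carried into the sample size but not into the analysis. The only remedy named in 15.2 is a transformation, which changes the scale and so does not directly give an interval for the promised mean difference.

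**Working it through.** **Inputs from the protocol.** 264 v 132 analysed; effect size 0.3 SD; two-sided 5%; 80% power; 30% loss (15.1, 15.2).

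**The plan's own figures first.** At 1:1, n per arm = 2(1.960 + 0.842)²/0.3² = 174.4, so 175 as stated. At 2:1, control n = 3(1.960 + 0.842)²/(2 × 0.3²/2) = 261.6, so 262 + 131 = 393 against 396 stated. Power at 264 v 132: 0.3/√(1/264 + 1/132) − 1.960 = 0.854, giving 80.4%. Loss: 264/0.7 → 378 and 132/0.7 → 189, total 567. All reproduce. They assume a common SD, so this point leaves them unchanged.

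**Standard error under unequal variances.** Let v be the residual variance in the intervention arm divided by that in the control arm.

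- True variance of the difference: v/132 + 1/264 = (2v + 1)/264.
- Ordinary ANCOVA variance: ((132v + 264)/396) × (1/132 + 1/264) = (v + 2)/264.
- Ratio of ordinary to true standard error: k = √((2 + v)/(1 + 2v)).
- Actual two-sided error at equal means: 2(1 − Φ(1.96k)).

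| v | k | Actual error |
|---|---|---|
| 0.5 | 1.118 | 2.8% |
| 1 | 1.000 | 5.0% |
| 1.5 | 0.935 | 6.7% |
| 2 | 0.894 | 8.0% |

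At 1:1 the ratio is (1 + v)/(1 + v) = 1 for every v, so the unequal allocation creates the sensitivity. A simulation of ANCOVA at 264 v 132 (8,000 runs per case) over SD ratios from 0.5 to 2 agreed. The ordinary test's type I error ran from 1.7% to 10.6%, and with HC3 it stayed between 4.6% and 5.2%.

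**Percent days abstinent.** Assumption: variance 0.49·m(1 − m) for mean m, and a shift of 0.3 SD. For a control mean of 70%, SD = √(0.49 × 0.21) = 0.321 and the intervention mean is 0.796. Then v = 0.796 × 0.204/0.21 = 0.77, k = 1.044 and coverage is 95.9%. Over control means of 30–70%, coverage is 94.5–95.9%; at 80% it is 96.5%. A separate simulation with U-shaped 28-day percentages gave 93.8–96.7% for ordinary intervals and 94.5–96.3% for HC3, over control means of 20–80%.

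**Criminal justice counts.** Assumption: negative binomial with variance m + φm², control mean 1 to 4 and φ from 0 to 2. Power, where the correct standard error would give 80%, is Φ(1.960 + 0.842 − 1.96k). Worked case, control mean 1, φ = 1, rate ratio 0.75: v = (0.75 + 0.5625)/2 = 0.656, k = √(2.656/2.3125) = 1.072, power 75.8%.

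| Rate ratio | k | Consequence |
|---|---|---|
| 1 | 1.000 | none; error 5.0% |
| 0.75 | 1.049–1.092 | SE 5–9% too wide; power 77.2–74.6% |
| 0.6 | 1.087–1.160 | SE 9–16% too wide; power 74.9–70.1% |
| 1.25 | 0.964–0.932 | SE 4–7% too narrow; coverage 94.1–93.2% |

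The formula depends only on the 2:1 ratio, so it also applies at 378 v 189. Simulations at that size assumed 36% of controls with an event and a control mean of 0.8 or 1.2. With 30% fewer events, power was 43% (ordinary) v 51% (HC3) at mean 0.8, and 35% v 46% at mean 1.2. With 40% fewer events, it was 74% v 80% and 63% v 72%. With identical distributions both tests held 4–6%.

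**The case against.** The strongest reply is that this is SAP detail. The protocol names ANCOVA and does not state a pooled variance; ANCOVA with robust standard errors would comply fully with 15.2 and 15.4. A reader might infer that the protocol commits to the pooled form, but that is only the default meaning of the term. This stands, and it is a main reason for the low priority. What remains is that the method, read in its usual sense, has a better alternative at almost no cost.

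A second reply is that 15.2 already provides for checking assumptions, and that criminal justice outcomes appear in 9.4 among the secondary measures, so the same check may reach them. That is fair. But the only action named after the check is transformation, which does not directly serve the promised mean difference, and 15.4 sets out its own method without a safeguard.

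A third concerns type I error. A reader might take the 6.7% and 8.0% above as what to expect in this trial. The documents do not support that. Those figures need a more variable intervention arm at equal means. If variance simply follows the mean, no effect implies equal variances and a 5% error rate. Section 15.2 does plan interaction terms with allocated group, so varying response is contemplated, but nothing in the protocol indicates its size or direction. This objection stands.

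**Conclusion.** The point holds as a conditional one of low priority. Under 2:1 allocation, ordinary ANCOVA standard errors are wrong if the arms' residual variances differ, and 15.2 and 15.4 do not allow for it. If the variances are equal, nothing is wrong.

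For percent days abstinent the effect is small: coverage of about 94–96% over most of the assumed range, and just under 97% at the extreme. For any criminal justice count analysed linearly, a true reduction of 25–40% in events would make the ordinary standard error roughly 5–15% too wide. A nominal 80% power would fall by about 3 to 10 points. The error is then conservative: real effects may be missed, not falsely claimed.

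A reader might conclude that the criminal justice counts suffer the largest loss. The documents do not establish that ranking. They give no mean or dispersion and do not say which outcomes receive the linear model. The ranking also depends on the assumptions: with control abstinence near 80%, the primary outcome's standard error is 7.6% too wide, similar to the counts at a rate ratio of 0.75. The 36% used in the simulations equals the recidivism estimate in section 6.2, which is not an event rate for this trial's population.

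**What to change.** State in 15.2 and 15.4, or confirm in the SAP, that every linear ANCOVA reports the mean difference on the original scale with heteroscedasticity-robust (HC3) standard errors and the matching 95% interval. In 15.4, also say which criminal justice outcomes get the linear model, so that it is clear where this applies.

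The cost is one line of text and one software option. If the arm variances turn out equal, the price is at most a point or two of power. No change to the sample size, allocation or data collection is needed.
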